#### *Prescribing an anti-inflammatory food plan and assessment of current diet*

The Clinical Investigator will prescribe an anti-inflammatory food plan that consists of a high intake of fruits and vegetables (4-5 serving of each per day). The specific dietary requirements for adherence to the anti-inflammatory food plan incorporated in this 9-week integrative medicine intervention will include macronutrient levels similar to those of a Mediterranean diet, which breaks down to 40-50% carbohydrates, 15-20% protein, and 35-40 % fat. Such a diet is high in fiber, micronutrients, healthy fats, and antioxidants that may provide health benefits by reducing inflammation. The Clinical Investigator will present the macronutrient requirements, assess the current diet of the participant, and suggest modifications that will cause their diet to conform to study guidelines, such as reducing sugar as well as processed and fast foods. They will discuss removing trans fats and hydrogenated oils and replacing them with cold-pressed and unrefined oils. For simplicity and accuracy, participants will be advised to follow a "Mediterranean-style eating pattern," which is very searchable among recipe databases and websites, and more specific than the term "anti-inflammatory."

Participants will be provided an anti-inflammatory food plan that includes recipes, a guide for adding and reducing certain foods, and obtaining targeted macronutrient levels (see above) if modification of their current diet seems infeasible, or if they so desire. The student researcher will assess the cooking skills of participants and provide resources, as needed (i.e. YouTube channels, websites). They will discuss meal-planning, meal-prepping, and making a grocery list on a budget as needed. Additionally, participants will be contacted twice via phone or email by the student researcher to provide nutritional and psychosocial support, answer any questions, and facilitate adherence.

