### Secondary Outcome measures:

#### *Dietary Adherence/Food Tracking Feasibility (MyFitnessPal food tracking):*

- Dietary adherence will be measured by self-reported food tracking through Daily Nutrition Goals in the *MyFitnessPal* app and will be documented at 5 and 9 weeks through the Friends feature. Daily macronutrient contributions will be obtained as percentages of total intake. The suggested macronutrient breakdown for the food plan is 40-50% calories from a carbohydrate source, 35-40 % calories from fat, and 15-20% calories from protein. Weekly recorded consumption of the participant will be compared to this standard for an adherence score. For each of the three macronutrient categories, we will give 2 points if the percentage is within the required range and 1 point if the percentage is within 5% of the required range (maximum 6 points total). A score of 4 and above will be considered adherent to the food plan.
- The feasibility of food tracking will be measured by adherence to the recommended use of the app. A threshold of 3 days of reporting per week (including breakfast, lunch, dinner, and snacks) for the 9-week duration of the study will be considered adherent and should provide sufficient data to assess the observance of the recommended food tracking.

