### Exploratory measures:

#### *Pain Visual Analog scale (VAS), The Patient-Reported Outcomes Measurement Information System (PROMIS-29), and Dietary Adherence associations:*

#### **Protocol**

Study Title: Integrative Medicine for Hypermobility Spectrum Disorder (HSD) and Ehlers-Danlos (EDS) syndromes: A mixed-methods feasibility study (IMforHSDandEDS)

PI: [name]

IRB #: DH10320/PRAF

Approval Date: 03.03.21

Version: 3.0

- We will evaluate any associations between symptom severity, perceived pain, health-related quality of life, and dietary composition cross-sectionally and longitudinally over the course of the 9-week intervention.

*Patient Assessment of Chronic Illness Care+ scores (PACIC+) collection:*

- We will collect general perceptions and attitudes regarding the experiences of chronic illness care and living with chronic illness among patients with HSD and EDS at baseline and 9 weeks.
- The Patient Assessment of Chronic Illness Care (PACIC+) is a validated survey shown to have good reliability, internal consistency, and better psychometric characteristics than other surveys on patient satisfaction. It is designed to assess the experience and satisfaction within the chronic care model of healthcare, which often results in repeated appointments over a long time interval. It retrospectively assesses experiences of chronic illness care and living with chronic illness over the past 6 months.

*Health history and anthropometric measurements:*

- Biological information will be captured regarding the patients' previous medical health history, age, sex, and gender at the baseline screening. We will also document BMI, weight, height, and estimated energy requirement measurements at baseline. We will record patient self-reported weight at 5 and 9 weeks and track any changes that occur. Any abnormal BMI values will be monitored appropriately for safety, and any changes in these measures will be analyzed in accordance with the overall effectiveness of the diet.
- We will also document any other patient-reported symptoms that are experienced in addition to HSD or EDS throughout the 9 weeks and document any changes that occur.
- Any current pain medications or supplements that the participants are taking for pain will also be recorded.

*Beighton score: range of motion measurements*

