### **E.9 Statistical Analysis**

All measures collected in the study, including baseline characteristics and outcome measures, will be summarized using mean and SD (biomarkers, anthropometrics), median and IQR (Beighton score), or percentage within each level, for categorical variables. All statistical analyses will be performed at the National University of Natural Medicine.

For Specific Aim 1,

Feasibility of the 9-week integrative medicine intervention will be measured through recruitment and retention at each follow-up visit. Recruitment rate will be presented as the mean number of participants enrolled per month, with enrolment ceasing either after 4 months, or when n=20 participants have been enrolled. Retention will be calculated as the percentage of enrolled participants from whom follow-up data is obtained, at either the 5-week or 9-week visit.

For Specific Aim 2,

Adherence to the recommended diet will be assessed in different ways and tracked by macronutrient levels and dietary composition. In particular, we will assess:

- Percentage of days on which the diet recommendations were met; in order to satisfy this requirement, macronutrient distribution must meet all of the following:
  - Carbohydrates between 40-50%
  - Protein between 15-20%
  - Fat between 25-30 %
- Number of weeks in which recommendations were met at least 5 days;
- Whether recommendations were met on at least 75% of total days (Y/N)
- Mean of weekly adherence scores calculated over the 9-week study period.

Percentage of days and weeks adherent will be summarized across participants as median/IQR/range. We will also present the percentage of participants who met the threshold of 75% days adherent.

Feasibility of the 9-week integrative medicine intervention will also be measured through self-reported food plan satisfaction surveys that assess any negative outcomes, overall cost-prohibitiveness or

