### **Protocol**

Study Title: Integrative Medicine for Hypermobility Spectrum Disorder (HSD) and Ehlers-Danlos (EDS) syndromes: A mixed-methods feasibility study (IMforHSDandEDS)

PI: [name]

IRB #: DH10320/PRAF

Approval Date: 03.03.21

Version: 3.0

burden, support needed, and any barriers that are encountered with the recommended dietary modifications.

- Because these measures are reported as open responses, they will be thematically summarized for representative quotes, at each time point measured.

Adherence with dietary tracking will be assessed by:

- Percentage of total days on which dietary intake was documented. Self-reporting of daily dietary intake on at least 50% of total days will be considered adherent.
- Number of weeks on which intake was self-reported at least 3 days.

For Specific Aim 3,

We will test whether the integrative medicine education intervention reduced pain and improved health-related quality of life in patients with HSD or EDS. VAS pain scores and PROMIS-29 domain scores will be summarized across participants and time points as mean (SD).

Analysis of pain and HRQoL outcomes for Aim 2 will use paired t-tests to assess mean changes unless investigation of distributions indicates a need for nonparametric testing, in which case changes will be analyzed using Wilcoxon signed-rank tests.

For Exploratory Aim 1,

Any associations between pain, HRQoL, and diet will be assessed both cross-sectionally and longitudinally over the course of treatment. Cross-sectional associations of VAS pain score, PROMIS-29 domain scores, and dietary composition measures will be analyzed using Pearson correlations (or Spearman correlations for badly non-normal data). To assess associations of longitudinal changes, we will compute changes in each measure both from baseline to 5 weeks, and from baseline to 9 weeks, and we will similarly evaluate correlations between the changes over each time period.

Cross-sectional correlations assess the association of participants' ordinary diet with pain and health-related quality of life, while correlations of changes assess the association of dietary changes, in response to the treatment recommendations, with changes in pain and HRQoL over the same time frame.

We will also assess associations between age, race, sex, baseline symptoms, and changes in outcomes at follow-up, using Pearson correlations and independent t-tests, as appropriate.

For Exploratory Aim 2,

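### Exploratory Aim 1 reads signed changes in diet as response to the recommendations, but the recommendations are two-sided ranges, so its longitudinal correlations can miss an association with following the plan

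*Combined protocol and SAP*

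**What the plan says.** Section E.9, Exploratory Aim 1, sets the method: "Cross-sectional associations of VAS pain score, PROMIS-29 domain scores, and dietary composition measures will be analyzed using Pearson correlations", with Spearman as the alternative for badly non-normal data. For the longitudinal part, "we will compute changes in each measure both from baseline to 5 weeks, and from baseline to 9 weeks", and the changes are then correlated with each other. E.9 gives the two parts different meanings. The cross-sectional correlations concern participants' ordinary diet, whereas "correlations of changes assess the association of dietary changes, in response to the treatment recommendations, with changes in pain and HRQoL".

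The recommendations are ranges. E.5 gives "40-50% carbohydrates, 15-20% protein, and 35-40 % fat". E.6, under dietary adherence, repeats them ("The suggested macronutrient breakdown for the food plan is 40-50% calories from a carbohydrate source", and so on) and defines a weekly score of 0 to 6 that treats deviations above and below a range alike. E.9 lists that score under Aim 2 as a descriptive summary.

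The dietary variable for Exploratory Aim 1 is not defined further. The E.6 heading for this analysis ends "and Dietary Adherence associations", but the bullet beneath it, and E.9, speak of dietary composition.

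**The concern.** With a two-sided target, two participants can follow the plan equally well and have changes of opposite sign. One who goes from 60% to 45% carbohydrate and one who goes from 32% to 45% have both done what was asked. Their raw changes are -15 and +13 points. If both have less pain, a linear or rank correlation of signed change sets one against the other.

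Nothing in the plan keeps starting points on one side. No eligibility criterion concerns baseline macronutrient intake, and the lead-in week records whatever the participant ordinarily eats.

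What is at stake is interpretation. A correlation near zero could be reported as showing that response to the recommendations is unrelated to pain, when it reflects only where participants happened to start. The sign of the correlation has the same weakness. Section F says the methods may be carried into a larger study, so the reading should be right.

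**Working it through.** E.9 states no expected correlation, SD or power for this aim, so there is no figure of the plan's own to reproduce. The check asks what each variable can detect.

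**Definitions.** For a nutrient with range L to U, the distance is d(x) = max(L - x, 0) + max(x - U, 0). Raw change is x(follow-up) - x(lead-in). Change in distance is d(follow-up) - d(lead-in).

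**Four participants, carbohydrate range 40-50%.** Pain change is set to 0.2 per point of change in distance.

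| Lead-in to follow-up (%) | Raw change | Change in distance | Pain change |
|---|---|---|---|
| 30 to 40 | +10 | -10 | -2 |
| 35 to 40 | +5 | -5 | -1 |
| 55 to 50 | -5 | -5 | -1 |
| 60 to 50 | -10 | -10 | -2 |

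Mean raw change is 0 and mean pain change is -1.5. The sum of cross-products is 10(-0.5) + 5(0.5) + (-5)(0.5) + (-10)(-0.5) = 0, so r = 0.00 with raw change. Pain change is exactly 0.2 times change in distance, so r = 1.00 with distance.

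**How much depends on the starting point.** The simulation used 1,500 replicates per scenario and carbohydrate alone. From the documents: the 40-50% range, n = 20, and n = 15 (0.75 × 20, the retention goal). Assumed: lead-in SD 10 points; movement by a random fraction (uniform 0 to 1) toward the nearest edge; follow-up noise SD 1.5; pain slope 0.2 per point of distance; residual pain SD 1.0; two-sided p < 0.05.

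| Lead-in mean | Below / above range | n = 20: mean r raw / distance | n = 20: p < 0.05 raw / distance | n = 15: mean r raw / distance |
|---|---|---|---|---|
| 35% | 69% / 7% | -0.61 / 0.66 | 83% / 91% | -0.61 / 0.67 |
| 45% | 31% / 31% | 0.01 / 0.52 | 21% / 68% | -0.03 / 0.51 |
| 50% | 16% / 50% | 0.37 / 0.57 | 48% / 77% | 0.38 / 0.56 |
| 55% | 7% / 69% | 0.61 / 0.67 | 83% / 92% | 0.60 / 0.66 |
| 60% | 2% / 84% | 0.74 / 0.76 | 97% / 98% | 0.73 / 0.74 |

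The loss is complete with balanced starts, partial with mixed starts, and negligible when nearly all start on one side. The sign of the raw correlation follows the starting side. At a mean of 45% the set-up is symmetric, so the 21% of runs with p < 0.05 for raw change fall about equally on either sign.

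**The mirror case.** A second simulation summed distance over the three nutrients. Assumed: n = 20; carbohydrate SD 7.5; protein SD 3.5; movement by a random fraction toward 45/17.5/37.5. Pain change was correlated 0.6 first with change in distance, then with raw carbohydrate change (protein mean 16% assumed there).

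| Lead-in carbohydrate mean | Pain follows distance: r raw / distance | Pain follows raw change: r raw / distance |
|---|---|---|
| 45% | -0.04 / 0.61 | 0.61 / -0.06 |
| 48% | 0.25 / 0.61 | 0.61 / 0.23 |
| 52% | 0.48 / 0.61 | 0.61 / 0.48 |

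Repeat runs of the first case at 45% gave raw r between -0.07 and 0.01. Spearman was no better (r 0.01, p < 0.05 in 7% of runs). Each variable misses what the other detects.

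**The fat range.** E.4.4, E.5 and E.6 give 35-40%. E.8 gives 25-30%, and E.9 under Aim 2 has "Fat between 25-30" per cent. In the single-nutrient simulation (n = 15, fat SD 7 assumed, pain driven by distance), a lead-in mean of 32.5% gives raw r = -0.40 against the 35-40% range and +0.40 against 25-30%. A range-based measure cannot be computed until one range is settled.

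**The case against.** The strongest reply is that Exploratory Aim 1 asks about diet and names dietary composition in section B, E.6 and E.9. Section B also says the exploratory aims can be viewed apart from treatment effects. Whether less carbohydrate or more fat goes with less pain is a directional question, and signed change is the natural variable for it. A simulation in which pain is built on distance must favour distance, and the mirror case shows that distance fails equally badly when pain follows the nutrient itself.

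All of this stands. A reader might infer that E.9 uses the wrong variable and that distance should replace raw composition throughout. The documents do not support that: it would change the question, and the cross-sectional analysis concerns ordinary diet before any plan is followed.

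A reader might also infer that E.9 rules out any adherence measure. That is too firm, since the composition measures are undefined and the E.6 heading mentions adherence.

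What the reply does not remove is the interpretive sentence. It could mean only changes that occur after the recommendations are given. But it ties the correlations to the recommendations, and those are ranges that signed change cannot represent.

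**Conclusion.** The concern holds for the longitudinal analysis and its interpretation. Signed change answers a directional question. It does not measure movement toward a two-sided target, and a real association with following the plan can appear as near zero when participants start on both sides.

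The size runs from total loss (mean r about 0 against 0.5 to 0.6) to almost none (0.74 against 0.76). It depends on a lead-in distribution that the documents do not give, and on the assumption that any benefit comes from closeness to the plan. It would go too far to say that the planned analysis will produce a false null.

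The point is minor: the aim is exploratory, there are at most 20 participants, and no primary, secondary or tertiary result changes.

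**What to change.** 1. The sponsor reconciles the fat range across E.4.4, E.5, E.6, E.8 and E.9 before any range-based measure is computed.
2. In the longitudinal part of Exploratory Aim 1 only, add the change from the lead-in week to weeks 5 and 9 in a range-based measure, as the exposure for response to the recommendations. It can be the summed percentage points outside the three ranges, or the E.6 adherence score. The score is already defined but coarser: in the balanced single-nutrient simulation at n = 20 its mean r was -0.31 (a higher score going with less pain), against 0.52 for distance.
3. Keep raw composition changes as the directional analysis, and leave the cross-sectional analysis on raw composition.
4. Reword the E.9 sentence so that only the range-based correlation is read as response to the recommendations, and name the variables meant by dietary composition measures.

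The cost is one derived variable and a few sentences, with no new data. The downside is one more set of exploratory correlations in at most 20 participants. A summed distance also hides which nutrient drives it, which the retained raw changes would show.

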## B. SPECIFIC AIMS

**B.1 Primary Aim:** To investigate the feasibility of a 9-week integrative medicine intervention, as assessed by recruitment and retention in patients with Hypermobility Spectrum Disorder (HSD) or Ehlers-Danlos syndromes (EDS).

- Outcome Measures 1: The recruitment rate will be assessed as the number of participants enrolled per month, over the duration of open recruitment. Our goal is to recruit 20 participants within a span of 4 months. Retention rate will be determined as the proportion of participants completing the mid-study or end-of-study visits, with a goal of 75% retention for each study visit.

**B.2 Secondary Aim:** To evaluate the feasibility of and adherence to a prescribed food plan as well as the feasibility of food tracking as a part of a 9-week integrative medicine intervention in patients with Hypermobility Spectrum Disorder (HSD) or Ehlers-Danlos syndromes (EDS).

- Outcome Measures 2: To assess the feasibility of the dietary recommendations, adherence will be assessed using estimated daily dietary intake recorded in *MyFitnessPal*, a food tracker app for mobile devices and computers. The participant's reported macronutrient breakdown will be compared to the prescribed food plan to calculate an adherence score. Participants will also complete a food plan satisfaction survey at baseline, 5, and 9 weeks that will examine any physical side-effects, support needed, and any barriers to adherence, including food costs. The feasibility of food tracking will be measured by adherence to the recommended use of the app. A threshold of 3 days of reporting per week (including breakfast, lunch, dinner, and snacks) for the 9-week duration of the study will be considered adherent and should provide sufficient data to assess the observance of the recommended food tracking.

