## Protocol

Study Title: Integrative Medicine for Hypermobility Spectrum Disorder (HSD) and Ehlers-Danlos (EDS) syndromes: A mixed-methods feasibility study (IMforHSDandEDS)

PI: [name]

IRB #: DH10320/PRAF

Approval Date: 03.03.21

Version: 3.0

**B.3 Tertiary Aim:** To examine the effect of a 9-week integrative medicine intervention on overall perceived pain and quality of life in patients with Hypermobility Spectrum Disorder (HSD) or Ehlers-Danlos syndromes (EDS).

- Outcome Measures 3: Participants will complete a Visual Analog Scale for Pain (VAS Pain) and a 29-Item profile HRQoL Survey (PROMIS-29) at baseline, 5, and 9 weeks.

In order to better understand the needs of the patient population, we will also address the following exploratory aims, as far as we are able. These aims can be considered to be independent of the effects of treatment.

**B.4 Exploratory Aim 1:** To evaluate any associations between symptom severity, perceived pain, quality of life, and diet among patients with Hypermobility Spectrum Disorder (HSD) or Ehlers-Danlos syndromes (EDS).

- Participants will be given a 1-week lead-in to establish baseline food patterns before starting the prescribed food plan. Associations of dietary composition, patient-reported symptoms, as well as overall perceived pain and quality of life scores will be examined, both cross-sectionally at intake and longitudinally over the 9 weeks of the intervention.

**B.5 Exploratory Aim 2:** To assess the experiences of chronic illness care and living with chronic illness among patients with Hypermobility Spectrum Disorder (HSD) or Ehlers-Danlos syndromes (EDS).

- Outcome Measure 5: Participants will complete a 26-item survey, Patient Assessment of Chronic Illness Care (PACIC+), that evaluates areas of patient self-management within the chronic care model of healthcare. The PACIC+ ascertains attitudes regarding patient-centered care, living with chronic illness, and chronic illness care; it will be completed by participants at baseline and 9 weeks.

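### Exploratory Aim 1 leaves open correlating an outcome's own baseline with its own raw change, which builds in a negative correlation with no true predictor of response

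*Combined protocol and SAP*

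**What the plan says.** Under Exploratory Aim 1 in E.9, "we will compute changes in each measure both from baseline to 5 weeks, and from baseline to 9 weeks". The last sentence of that block will relate age, race and sex, along with "baseline symptoms, and changes in outcomes at follow-up, using Pearson correlations and independent t-tests". E.9 gives no baseline-adjusted model, no significance level and no note on regression to the mean for this analysis.

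The term baseline symptoms is not defined. B.4 names symptoms as a separate item ("Associations of dietary composition, patient-reported symptoms, as well as overall perceived pain and quality of life scores will be examined"), and the exploratory measures in E.6 likewise speak of "associations between symptom severity, perceived pain, health-related quality of life, and dietary composition cross-sectionally and longitudinally". E.6 also adds unscored material: "We will also document any other patient-reported symptoms that are experienced in addition to HSD or EDS throughout the 9 weeks". The only scored symptom-type measures that E.9 analyses are VAS pain and the PROMIS-29 domains, and they are also the outcomes whose change is taken.

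**The concern.** Change is follow-up minus baseline, so the baseline score enters the change with a negative sign. If the same score is then used as the baseline symptom, the two variables share a component of opposite sign. They correlate negatively even when every participant has the same expected response.

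The error has a predictable direction: participants who start worse appear to benefit more. The study has one arm, so no control group would show the same pattern without treatment and expose it. A reader could take the result for a responder profile.

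**Working it through.** The plan states no error rate or expected correlation for this analysis, so there is no figure of its own to reproduce.

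**Inputs from the protocol**
- Enrolment target 20 (B.1: "Our goal is to recruit 20 participants within a span of 4 months").
- Retention goal 75% per visit (B.1), so 0.75 × 20 = 15 with a change score if the goal is just met.
- No preliminary data (D.1), so no correlation or SD is available.

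**Assumptions**
- Correlation ρ between baseline Y0 and follow-up Y1 of 0.5 to 0.8.
- Equal SDs, normal scores, two-sided 5% test.
- No predictor of response in any case.
- Rejection rates are from simulation with 40,000 replicates per setting (simulation standard error at most √(0.25/40,000) = 0.25 percentage points).

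**Case 1: the symptom is the outcome's own baseline.** With unit SDs, cov(Y0, Y1 − Y0) = ρ − 1 and var(Y1 − Y0) = 2(1 − ρ). Hence

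r = −(1 − ρ)/√(2(1 − ρ)) = −√((1 − ρ)/2).

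At ρ = 0.5 this is −√0.25 = −0.50. At ρ = 0.8 it is −√0.10 = −0.32.

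| ρ | expected r | rejects, n=15 | rejects, n=20 |
|---|---|---|---|
| 0.5 | −0.50 | 50% | 64% |
| 0.6 | −0.45 | 40% | 53% |
| 0.7 | −0.39 | 31% | 41% |
| 0.8 | −0.32 | 21% | 28% |

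With unequal SDs, k = SD(follow-up)/SD(baseline), r = (kρ − 1)/√(1 + k² − 2kρ). For ρ of 0.5 to 0.7 and n of 15 or 20, k = 0.8 gives 72% to 91% rejection and k = 1.2 gives 10% to 35%.

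**Case 2: a different symptom, correlated c with the baseline score and linked to follow-up only through that observed score.** Then r = −c√((1 − ρ)/2). For c = 0.5 and ρ = 0.5 this is −0.25.

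| c | ρ = 0.5, n=20 | ρ = 0.7, n=20 | ρ = 0.8, n=20 |
|---|---|---|---|
| 0.5 | 19% | 13% | 10% |
| 0.7 | 34% | 21% | 16% |

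At c = 0.2 to 0.3 the rate is about 5.5% to 10% over n of 15 and 20. Adjusting for the outcome's own baseline brings this case back to about 5%.

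**Case 3: a different symptom that tracks only the participant's stable level.** The symptom then has the same covariance with Y0 and Y1, which cancels in the difference, so r = 0. Raw change rejects about 5% of the time. Here it is the baseline-adjusted analysis that misleads. Its partial correlation is c(1 − ρ)/√((1 − ρ²)(1 − c²)), which for c = 0.5 and ρ = 0.5 is 0.25/√(0.75 × 0.75) = +0.33. At n=20 and ρ of 0.8 to 0.5 it rejects about 12% to 29% for c = 0.5, and 28% to 75% for c = 0.7.

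**Case 4: age, race or sex unrelated to the outcome's baseline.** About 5%.

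**Check of the alternative for Case 1.** Correlating change with the mean of baseline and follow-up (Oldham's method, equal SDs) rejects 4.8% to 5.2% of the time.

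**The case against.** The strongest reply is that the documents never say a baseline symptom is the outcome's own baseline score. B.4 and E.6 list symptoms apart from pain and quality of life, and other symptoms are recorded. For a chronic symptom that follows a stable level, raw change is sound, as Case 3 shows. All the rates rest on an assumed ρ, SD ratio and alpha, and the analysis is one supplementary sentence under an exploratory aim.

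Most of this stands, and it sets the limits of the point. It does not remove Case 1. The undefined term admits baseline VAS and PROMIS-29 scores, no passage rules them out, and they are the only scored symptom-type measures in E.9.

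Three stronger readings are tempting and are not supported:
- A reader might infer that any baseline variable related to baseline pain inherits the negative coupling. Case 3 shows that this fails when the link is through the stable level, and the documents do not say which kind of link applies.
- A reader might infer that baseline-adjusted regression should simply replace raw change, for age and sex as well. In Case 3 adjustment creates an artefact of its own, and age and sex need no correction unless related to baseline level.
- A reader might infer that the later study would be misdirected. Section F says only that the methods could carry over to a larger study. No passage uses predictors of response to choose participants.

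**Conclusion.** The point holds in limited form. For an outcome's own baseline against its own change, the negative correlation is built in whenever the SDs are equal and ρ is below 1, and nothing in the plan mitigates it. The rates in Case 1 are well above 5% but are conditional on the stated assumptions. A larger follow-up SD shrinks them and a smaller one enlarges them.

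For other baseline symptoms the inflation at n=20 lies anywhere from none to about 34% over the correlations examined, and the documents cannot settle where. The consequence is a misleading exploratory finding. Recruitment and retention, the primary aim, are not affected.

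**What to change.** In E.9, Exploratory Aim 1:

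- Define baseline symptoms by naming the measures.
- State that an outcome's own baseline will not be correlated with its own change. Adjustment cannot rescue this pair, since the baseline cannot be adjusted for itself. If the question is wanted, correlate change with the mean of baseline and follow-up, and say that this assumes equal SDs.
- State that no correlation of an outcome's own baseline with its own change will be read as prediction of response.
- For other baseline symptoms, keep the raw-change correlation and report beside it the association adjusted for the outcome's own baseline. Note that the two rest on different assumptions and that only agreement between them, in direction as well as presence, suggests a predictor. For a symptom positively related to the baseline score, the artefact is negative in the raw-change analysis and positive in the adjusted one.

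This takes a few sentences, no new data, a little more exploratory analysis, and one degree of freedom in each adjusted model.
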